Official Title: Influence of Edible Marijuana on Endurance Exercise Performance

NCT Number: NCT05192239, Unique Protocol ID: 2827

Document Date: 12/31/2022

#2827 - Influence of edible marijuana on endurance exercise performance

Protocol Information

Submission Type	Review Type	Status	Time in Current Status
Close Request	--	Closed	Since January 3 – 6 months
Initial Approval Date	Initial Review Type		
Nov 30, 2021	Full Board		

Close Comment

Thank you for informing the IRB that the work associated with this protocol is complete. To comply with federal regulations, please be sure to securely keep all research records, including signed informed consent documents, for a period of 3 years from this date.

Let us know if you have any questions.

[contact]

Feedback

Protocol Close Request Form

Close Request

Completed Date

December 31, 1969

Summary of Findings

A manuscript was accepted for publication in the journal, *Frontiers In Physiology*. Here is the title and abstract: **Edible marijuana and cycle ergometer exercise**

Purpose: There is extensive public and scientific interest in the influence of cannabis and the psychoactive cannabinoid, delta-9-tetrahydrocannabinol (THC), on exercise performance. Unfortunately, recent, up-to-date studies are lacking. The aim of the current study was to address the hypothesis that ingestion of edible marijuana, prior to exercise, would have unfavorable effects on the physiological response to exercise and on exercise performance.

Methods: 17 Healthy adult male and female habitual exercisers, who were regular users of cannabis products, were screened for study participation. 10 were enrolled, and data from 9 [8 males, 1 female, aged 25 ± 3 years, with peak oxygen uptake of 56.5 ± 11.7 ml/kg/min (mean \pm SD)] were retained. Participation included two exercise sessions, each preceded by self-administration and ingestion of either edible marijuana (containing 10 mg THC) or placebo. Cardio-respiratory responses (via indirect calorimetry) to stationary cycle ergometer exercise (8 min at 50, 100 and 150 W) were recorded before completion of a 20-min Functional Threshold Power test (FTP20) and a sprint test involving maximal effort until volitional fatigue.

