Results: Edible marijuana increased the concentration of circulating THC and THC metabolites, and evoked sensations of intoxication and altered psychoactive state. Cardio-respiratory responses to staged cycle ergometer exercise were normal and were unaffected by edible marijuana. Compared with placebo, edible marijuana did not influence FTP20 (Placebo 253 ± 75 vs THC: 251 ± 72 W (mean \pm SD); $p > 0.45$) or peak power output during the sprint test (Placebo: 710 ± 201 vs. THC: 732 ± 136 W; $p = 0.864$). **Conclusion:** 10 mg of THC, when ingested prior to exercise by regular exercisers and habitual users of cannabis, had little effect on the physiological response to standardized cycle ergometer exercise, and was neither ergogenic nor ergolytic. The manuscript is available here: <https://pubmed.ncbi.nlm.nih.gov/36545283/>

In the box below, please attach any relevant publications that resulted from the data collection for this study, and/or any other relevant documentation that should be kept with this file.

Close Request Questions

Completed As Planned?

Yes

Please state the number of participants enrolled in this study.

17

Please state the number of participants who completed this study.

10

Please state the number of participants who withdrew from this study.

7

Were there any unanticipated problems or adverse events that were *not previously* reported to the IRB?

No

General Information

Principal Investigator

[name]

Lead Unit

Health + Exercise Science (CO-1582)

Title

Influence of edible marijuana on endurance exercise performance

People**People****Person**

[name]

Home Unit

Health + Exercise Science (CO-1582)

Email Address

[contact]

Phone**CSU Status****Researcher Role**

Principal Investigator

Contact Roles

Admin

Permissions

Full Access

People Attachments

Person

[name]

Home Unit

Health + Exercise Science (CO-1582)

Email Address

[contact]

[contact]

CSU Status

Other

Researcher Role

Key Person

Contact Roles

Permissions

Full Access

People Attachments

Person

[name]

Home Unit

Health + Exercise Science (CO-1582)

Email Address

[contact]

Phone**CSU Status****Other****Researcher Role**

Key Person

Contact Roles**Permissions**

Full Access

People Attachments**Person**

[name]

Home Unit

Health + Exercise Science (CO-1582)

Email Address

[contact]

[contact]

CSU Status

Other

Researcher Role

Key Person

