The purpose of the proposed project is to provide athletes and the scientific community with data pertaining to the acute influence of edible marijuana on exercise performance, and the physiological responses to standardized exercise. Specifically, we wish to determine: 1. The influence of edible marijuana on cardio-respiratory and metabolic responses to standardized cycle ergometer exercise. 2. The influence of edible marijuana on endurance exercise (time-trial) performance.

What do the investigators hope to learn from the project?

We wish to determine if edible marijuana, ingested prior to exercise, is ergogenic (improves performance) or ergolytic (decreases performance). We hypothesize that edible marijuana will be ergolytic.

Describe how sharing results of this study could influence behavior, practice, theory, future research designs. Specifically, how will study results apply to a larger population than the studied participants?

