## Statistical Analysis Plan

All data, unless otherwise stated, are expressed as mean and standard deviation. To compare baseline values between placebo and edible marijuana for circulating concentrations of THC, and THC metabolites, one-way analysis of variance (placebo vs edible marijuana) was used, unless a non-parametric equivalent (i.e. one way analysis of variance on ranks) was required on account of unequal variance. The standardized exercise statistical analysis was conducted in R (R Core Team; Vienna, Austria) as linear mixed models using the Lmer and LmerTest packages (Bates et al., 2015), and Emmeans package was used for post hoc Tukey testing to explore main effects and interactions. Time and Condition were considered fixed effects, whereas Subject was considered a random effect to account for the repeated measures. Unlike an electrically braked ergometer, it is not feasible to externally fix the work rate on an air braked ergometer; the actual work rate is determined by the damper setting and the participant's pedal cadence. During the standardized exercise test, participants were instructed to exercise at 50, 100 and 150 W. Accordingly, for statistical analysis of these data, work rate error, defined as the difference between the prescribed work rate and the actual work rate, was considered as a covariate in our model. One- and two-way analysis of variance, with repeated measures, were employed to detect differences among variables during the performance of the FTP20 and in the sprint to fatigue tests using SigmaPlot 14.5 (Systat Software Inc., San Jose, California). Specifically, one-way repeated measures ANOVA was used to compare mean work rate (placebo vs edible marijuana). Two-way ANOVA with repeated measures (time) was used to compare power outputs across consecutive stages (placebo vs edible marijuana). One-way repeated measures ANOVA was used to compare mean power, peak power, time to fatigue, and total work done (placebo vs edible marijuana) during the sprint to fatigue tests. Significance was defined as  $p < 0.05$ . Wherever a significant difference was detected, a post-hoc Tukey test was utilized to further explore these differences.

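### The peak-power p-value of 0.864 cannot come from the SAP's paired test on 9 complete pairs, and a non-significant difference does not show that no effect exists

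*Protocol*

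**What the plan says.** The results appear in the abstract under Summary of Findings in the protocol's Close Request form. On numbers it states "10 were enrolled, and data from 9" were retained. Peak power in the sprint is given as "Placebo: 710 ± 201 vs. THC: 732 ± 136 W; $p = 0.864". FTP20 is 253 ± 75 W on placebo and 251 ± 72 W on THC, with p > 0.45. The conclusion is that 10 mg THC "was neither ergogenic nor ergolytic". That answers the question in the protocol's Summary and Purpose: "We wish to determine if edible marijuana, ingested prior to exercise, is ergogenic (improves performance) or ergolytic (decreases performance".

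The SAP fixes how these figures should be read. On format: "All data, unless otherwise stated, are expressed as mean and standard deviation". On the sprint: "One-way repeated measures ANOVA was used to compare mean power, peak power, time to fatigue, and total work done". For FTP20 it names two analyses: "Specifically, one-way repeated measures ANOVA was used to compare mean work rate (placebo vs edible marijuana", and "Two-way ANOVA with repeated measures (time) was used to compare power outputs across consecutive stages". Significance is p < 0.05. The SAP text names a rank-based alternative only for baseline THC and metabolite concentrations. The documents give no equivalence margin, smallest worthwhile change or confidence interval for any performance outcome.

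**The concern.** There are two linked points.

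First, the printed p-value looks too large for the printed means and SDs. A 22 W difference on 9 pairs can give a p this close to 1 only if the within-person differences are extremely variable, and the two SDs limit how variable they can be.

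Second, the conclusion says that no effect exists in either direction, while the only rule behind it is a test for a difference. Failing to reject in 9 people does not rule an effect out.

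Together, these leave a reader unable to tell which people or which test produced the peak-power figure, or how large an effect the data leave open. Meanwhile the conclusion reads as a settled answer to the study's question.

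**Working it through.** **Inputs.** Means 710 and 732 W, SDs 201 and 136 W, p = 0.864, and 9 participants retained (abstract); one-way repeated-measures ANOVA, and ± as SD (SAP); crossover design (protocol, Procedures). The number of sprint pairs is not printed separately; 9 is the natural reading. The within-person correlation r is not given, so its whole range is used.

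**Formula.** With two conditions, F(1, n-1) = t², so the planned test is the paired t-test:

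SD_diff = sqrt(201² + 136² - 2·r·201·136), t = 22·sqrt(n)/SD_diff, df = n - 1, two-sided.

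**Attempt to reproduce 0.864 with n = 9.**
- r = +1: SD_diff = 201 - 136 = 65; t = 22·3/65 = 1.015; p = 0.340.
- r = -1: SD_diff = 201 + 136 = 337; t = 22·3/337 = 0.196; p = 0.850. This is the largest p possible from the printed values.
- Rounding all in favour (difference 21 W, SD sum 338 W): p = 0.857.
- Working back: p = 0.864 on 8 df needs t = 0.1769, so SD_diff = 66/0.1769 = 373 W, above the 337 W maximum. With favourable rounding it needs 63/0.1769 = 356 W, above 338 W.

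The figure is not reproduced at any correlation.

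**Simple alternatives.**
- All 10 enrolled, paired: t = 22·sqrt(10)/337 = 0.206; maximum p = 0.841 (0.849 with favourable rounding).
- Unpaired, 9 vs 9: t = 22/sqrt((201² + 136²)/9) = 0.272; p = 0.789 (Welch 0.790).
- Rank tests on 9 pairs: exact Wilcoxon steps from 0.820 to 0.910; its normal approximation comes closest at 0.859; Friedman without ties gives 0.739 or 0.317. None gives 0.864.
- Fewer pairs, with means, SDs and test all on the same people:

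| Pairs | r needed for p = 0.864, printed values |
|---|---|
| 8 | not attainable (maximum p 0.859); with favourable rounding (maximum 0.865), r of about -0.94 or lower |
| 7 | -0.86 |
| 6 | -0.56 |
| 5 | -0.25 (about -0.12 with favourable rounding) |
| 4 | +0.06 |

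So from 5 pairs upward, a common set requires people who were strong in one sprint to be weak in the other. If the means and the p-value do not share one set, they describe different people.

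**What the planned test would give, and the interval, on 9 pairs.** The 95% half-width is 2.306·SD_diff/3. The values of r below +1 are assumptions.

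| r | SD_diff (W) | p | 95% CI (W) |
|---|---|---|---|
| 0.5 | 178 | 0.72 | -115 to +159 |
| 0.8 | 123 | 0.61 | -73 to +117 |
| 0.9 | 98 | 0.52 | -54 to +98 |
| +1 (narrowest possible) | 65 | 0.34 | -28 to +72 |

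The narrowest interval is -28/710 = -4% to +72/710 = +10% of the placebo mean.

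**FTP20.** Suppose p > 0.45 comes from the one-way comparison of mean work rate on 9 pairs. Then |t(8)| < 0.794, so SD_diff > 2·3/0.794 = 7.55 W, and the 95% half-width exceeds 2.306·7.55/3 = 5.8 W around the printed 2 W difference. If rounding makes the true difference 1 or 3 W, the bound is 2.9 or 8.7 W. This is only a lower limit on width; the interval itself cannot be recovered from an inequality.

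**The case against.** The strongest reply is that the number of sprint pairs is inferred. The sprint was maximal and came last, so missing sprint data are possible, and 8 pairs can just reach 0.864. The shortfall at the limit is also small (0.857 against 0.864), and the larger contrast with 0.52 to 0.72 rests on assumed correlations. This stands as far as it goes: the arithmetic shows an inconsistency, not its cause. But 8 pairs work only with favourable rounding and a correlation near -1, and if the sprint set was smaller, its size needs stating.

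The intervals above take the printed means, SDs and n as correct, although part of that set must be wrong or incomplete. That is a fair caveat, and the intervals are conditional on it.

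The text is an abstract, and the full paper, which is not among the documents, may give the test, the pairs and the intervals. That is possible. Even so, the abstract's conclusion goes beyond what the SAP's criterion can show. Its restriction to 10 mg in habitual users and regular exercisers, and its accompanying mention of little effect, narrow the claim but do not supply an interval.

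Finally, the consequence is limited. No attainable p on 9 pairs is significant, and peak power is not one of the two aims in Summary and Purpose. Both points are accepted.

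**Conclusion.** Both points hold. With the SAP's test on 9 complete pairs, p = 0.864 lies outside the range the printed means and SDs permit (0.340 to 0.850, or 0.857 at the rounding limit). This needs no assumption about correlation; it rests only on 9 complete pairs, ± meaning SD, and the planned test. Fewer or unequal sprint observations, a different test, or an error in a mean, an SD or the p-value could each explain it. The non-significant verdict on peak power does not change.

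The claim of no effect in either direction is not supported by a difference test at p < 0.05 with no margin and no interval. Taking the printed figures at face value, even the narrowest peak-power interval runs from -28 to +72 W. FTP20 may be estimated more tightly, but the abstract does not give enough to show it. Because the documents state no smallest worthwhile change, it is not claimed that effects of this size matter in practice. What the reported results support is that no difference was detected.

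**What to change.** 1. Check peak power against the raw data. Either correct the p-value, or state the test used and the number of pairs and give means and SDs for those same pairs.
2. In the SAP, require the paired mean difference with its 95% CI and number of pairs for FTP20 and for each sprint outcome. Give the exact FTP20 p-value and say which of the two FTP20 analyses it comes from.
3. Reword the conclusion along these lines: no difference was detected, and effects of up to X W are not excluded, with X taken from the interval. Keep a claim of no effect only if the interval lies inside a justified smallest worthwhile change.
4. As a minor clarification, reconcile the abstract, which has 17 screened and 10 enrolled, with the Close Request Questions, which have 17 enrolled, and state why data from one of the 10 were not retained.

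The cost is one re-check of existing data, a few more reported figures and a reworded sentence. No new data are needed. The price is a less definite conclusion.

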Clinical Trial

Will participants will be prospectively assigned to one or more interventions (including placebo or other control)?

Yes

Will the study evaluate the effects of the intervention on health-related outcomes (biomedical or behavioral)?

Yes

Does this study involve an FDA-regulated drug or device?

No

Will the study be conducted as a
Single-Site Clinical Trial

Will this study be posted on ClinicalTrials.gov?

Yes

ClinicalTrials.gov Registration# (or pending)

Pending

Additional information and support available through CSU Quality Assurance:
[contact]

Participant Population

Are you interacting or intervening with participants?

Yes

Provide an estimate of the anticipated participant total.

30

Are you analyzing existing data records or biospecimens?

No

Inclusion and Exclusion Criteria (e.g., Participants must have 20/20 vision, Participants must be 30-45 years of age, etc.) This should match your screening, consent, and recruitment materials.

Please list all inclusion criteria

Age 21-40 years, inclusive Body mass greater than 110 lbs (50 kg) Habitual user of cannabis; average use cannabis is minimum of once per month during the previous year Prior use of cannabis product containing at least 10 mg of THC with no adverse reaction Habitual exerciser: exercised a minimum of 5 days per week, for a minimum of 30-minutes/session, during the previous year.

Please list all exclusion criteria

Identification of a contra-indication to exercise during a 12-lead exercise stress test. Pregnant or trying to become pregnant. Breastfeeding. Recipient of treatment for psychotic or bipolar disorder during the previous 2 years Recipient of treatment for Schizophrenia during the previous 2 years Planned surgery scheduled within 2-weeks of study participation

What is the rationale for studying the requested group(s) of participants?

Rationale for the inclusion criteria: Legal age limit for cannabis use in Colorado is 21 years. Body mass greater than 50 kg to remain compliant with IRB for repeated blood sampling. Habitual use of cannabis and prior use of cannabis containing 10 mg of THC: we wish to avoid potential side-effects and unpredictable reactions associated with first-time cannabis use. Habitual exerciser: this study will be most relevant to athletes and people regularly engage in exercise, thus we will recruit people who best fit this description.

Will you use a screening procedure, instruments, tools, questionnaires etc.?

Yes

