Ingestion of Edible Cannabis (From WebMD and Drugs.com) (also see "Psychological Well-Being) Cannabis might cause fast heartbeat and high blood pressure. It might also increase the risk of a having heart attack. Certain chemicals in cannabis can weaken the immune system. This might make it more difficult for the body to fight infections. Cannabis might increase the risk of an allergic reaction in people with allergies to foods like tomatoes, bananas, and citrus fruit. It is unclear if cannabis worsens chronic liver disease. While some weak evidence suggests that there might be a link, other evidence has not found a link. Using cannabis after having a stroke might increase the risk of having a second stroke. Cannabis affects the central nervous system or the brain and nerves. It might slow the central

nervous system too much when combined with anesthesia and other medications during and after surgery.

Are there risks associated with psychological well-being?

Yes

Please describe.

Ingestion of Edible Cannabis (From WebMD and Drugs.com) (also see "Physical Well-Being) Use of cannabis is likely to lead to an altered state of consciousness. The user may feel "high", very happy, euphoric, relaxed, sociable and uninhibited. The user may experience distorted perceptions of time and space. The user may feel more sensitive to things around them, and may also experience a more vivid sense of taste, sight, smell and hearing. Using cannabis might make manic symptoms worse in people with bipolar disorder. Cannabis use, especially frequent use, might increase the chance of getting depression. It can also worsen symptoms of depression and increase thoughts about suicide in those that already have depression. Using cannabis might make symptoms of schizophrenia worse.

Are there risks associated with economic well-being, including employability?

Yes

Please describe.

Participants wishing to seek/maintain employment with institutes that frequently perform drug testing should not participate. Given that the participants will all be habitual users of cannabis, this risk is low and the situation unlikely.

Are there risks associated with social well-being, including reputational risks?

No

Describe how the benefits of the research justify the likely risks to participants.

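### A history of stroke is not an exclusion, although the protocol's own risk text warns about cannabis use after a stroke (low-priority safety improvement)

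*Protocol*

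**What the plan says.** The Protocol, Participant Population, asks for all exclusion criteria and gives six: a contra-indication to exercise found on the 12-lead stress test; pregnancy or trying to conceive; breastfeeding; "Recipient of treatment for psychotic or bipolar disorder during the previous 2 years"; treatment for schizophrenia over the same period; and surgery planned within two weeks of participation. Stroke is not mentioned.

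The risk description for edible cannabis, under Risks and Benefits, says: "Using cannabis after having a stroke might increase the risk of having a second stroke". It also gives a general cardiac warning: "It might also increase the risk of a having heart attack".

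Three other places bear on who gets in:

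- Procedures, Session 1, uses a medical history questionnaire and the graded exercise test with ECG to look for contra-indications, and follows a sports-medicine guideline on physician supervision.
- Privacy and Confidentiality says the medical history serves to find contra-indications, and refers the reader to the exclusion criteria.
- The screening text in Participant Population makes anyone willing who meets the enrollment criteria eligible.

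**The concern.** The protocol names a serious recurrent event in a group that one history question would identify, yet does not bar that group from dosing. Read literally, the criteria admit a volunteer with a past stroke who meets everything else. In one of Sessions 4 and 5 that person would take 10 mg THC, complete staged cycling, ride an all-out time trial and then sprint, typically in a home rather than the campus laboratory. The same risk text says cannabis may speed the heart and raise blood pressure. The stake is participant safety only; no endpoint, sample size or analysis depends on this.

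**Working it through.** **Step 1. Warned conditions against exclusions.** The risk text ties cannabis to seven specific conditions or situations. Set beside the exclusion list:

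| Condition or situation in the risk text | Exclusion listed? |
|---|---|
| Bipolar disorder: "Using cannabis might make manic symptoms worse in people with bipolar disorder" | Yes, if treated in the past 2 years |
| Schizophrenia: "Using cannabis might make symptoms of schizophrenia worse" | Yes, if treated in the past 2 years |
| Surgery and anesthesia | Yes, if planned within 2 weeks |
| Prior stroke: "Using cannabis after having a stroke might increase the risk of having a second stroke" | No |
| Depression: "It can also worsen symptoms of depression and increase thoughts about suicide in those that already have depression" | No |
| Food allergy: "Cannabis might increase the risk of an allergic reaction in people with allergies to foods like tomatoes, bananas, and citrus fruit" | No |
| Chronic liver disease: "It is unclear if cannabis worsens chronic liver disease" | No |

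Three of seven are matched and four are not. The general heart attack warning has no history-based exclusion either. The protocol therefore does not follow a rule that every warned hazard is excluded, and the case for stroke has to stand on its own.

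**Step 2. Could another written criterion catch a prior stroke?**

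- The only cardiovascular exclusion is what the exercise stress test reveals. An exercise ECG does not detect a past stroke.
- The medical history questionnaire might reveal one, but the protocol states no rule for acting on it, and the Privacy and Confidentiality text points back to an exclusion list without stroke.
- The inclusion criterion of having tolerated at least 10 mg THC has no time window, so that use could predate the stroke.

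**Step 3. Timing of exposure (Procedures, Sessions 2, 4 and 5).** Cycling starts 10 minutes after ingestion, runs for three 8-minute stages, and is followed by a 5-minute break before the time trial:

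10 + 3 × 8 + 5 = 39 minutes from ingestion to the time trial. The sprint follows after a further 5-minute break.

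**Step 4. How likely is such a volunteer?** The documents give no stroke prevalence. Let p be the proportion of otherwise eligible volunteers with a prior stroke, assumed to lie between 0.001 and 0.005. The chance of at least one among N people is 1 − (1 − p)^N.

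| N | Source of N | p = 0.001 | p = 0.005 |
|---|---|---|---|
| 30 | Anticipated total, Participant Population | 0.030 | 0.140 |
| 17 | Reported screened, closing abstract | 0.017 | 0.082 |
| 10 | Reported enrolled, closing abstract | 0.010 | 0.049 |

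The row for 17 counts people screened, not all of whom were dosed, so it is not an exposure figure. All these figures give the chance that such a person is present. The documents give no recurrence risk, so the chance of harm cannot be computed.

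**The case against.** The best case against is that this is preference rather than defect. The risk section is disclosure text, taken from general consumer sources and worded cautiously. It was not written as a list of exclusions, and four of its seven conditions have none. That stands as far as it goes: there is no broken rule here. But stroke can be singled out on the text itself, because it is described as a repeat of a serious event in people whom one question identifies, whereas the liver statement says only that the effect is unclear.

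Second, medical screening exists and its form is not visible. It may ask about stroke, and the cross-reference to the exclusion criteria does not say that only listed items count. This also stands, and limits the claim to the absence of a visible written rule. It does not remove the point: the protocol form says the listed criteria should match the screening materials, so a stroke question on the form should have a counterpart in the list.

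Third, the added exposure is small. Participants use cannabis at least monthly, have tolerated 10 mg or more of THC, abstain for 96 hours before each dosing session, and do the same exercise without THC in Sessions 2 and 3. For a frequent user, net cannabis exposure may not rise at all. What the trial adds is one 10 mg dose combined with maximal effort, and the stroke warning itself says nothing about exercise. This is a fair reason for low priority.

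Finally, the study is closed, so a change can only help a later protocol that reuses these criteria.

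**Conclusion.** The concern holds as a low-priority safety improvement. Stroke is warned of and not excluded, and no other visible written criterion would reliably exclude it. The affected group is very small: the chance that at least one such volunteer appears is 3% to 14% for 30 participants and 1% to 5% for 10, resting entirely on an assumed prevalence of 0.1% to 0.5%. The conclusion about the written list does not depend on that assumption. It would lose most of its practical force if the screening form already asks about stroke and the team acts on the answer. Nothing in the documents suggests that anyone with a prior stroke was enrolled or harmed.

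**What to change.** Add history of stroke to the exclusion criteria in Participant Population, and confirm that the screening questionnaire asks about it. As this study is closed, carry the change into any later protocol that reuses these criteria. The cost is one line in the list, one screening question if it is not already there, and at most a rare lost volunteer. Sample size, endpoints and analysis are unchanged.
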